6.2.1 Study treatment discontinuation criteria specific to tiragolumab or atezolizumab-related AEs

- Any Grade ≥ 2 treatment-related uveitis, eye pain, or blurred vision that does not respond to topical therapy and does not improve to Grade 1 severity within 8 weeks or requires systemic treatment.

- Any Grade ≥ 2 treatment-related pneumonitis or interstitial lung disease that does not resolve following dose delay and systemic steroids.
- For Grade ≥ 3 adrenal insufficiency or Grade ≥ 4 hypophysitis, treatment needs to be discontinued regardless of control with hormone replacement (Note: Hospitalization for diagnostic workup of adrenal insufficiency without severe symptoms should not require discontinuation).
- Any Grade ≥ 3 non-skin, treatment-related AE lasting > 7 days or recurs, with the following exceptions for uveitis, pneumonitis, bronchospasm, diarrhea, colitis, neurologic toxicity, hypersensitivity reactions, infusion reactions, endocrinopathies, and laboratory abnormalities:
 - Grade 3 treatment-related uveitis, pneumonitis, bronchospasm, diarrhea, colitis, neurologic toxicity, hypersensitivity reaction, or infusion reaction of any duration requires discontinuation.
 - Grade 3 treatment-related endocrinopathies (excluding adrenal insufficiency and hypophysitis) adequately controlled with only physiologic hormone replacement do not require discontinuation.
 - Grade 3 treatment-related laboratory abnormalities do not require treatment discontinuation except:
 - Grade 3 treatment-related thrombocytopenia > 7 days or associated with clinically significant bleeding requires discontinuation.
- In most cases of Grade 3 AST or ALT elevation, study treatment will be permanently discontinued. If the Investigator determines a possible favorable benefit/risk ratio that warrants continuation of study treatment, a discussion between the Investigator and the Medical Monitor/designee must occur.
- Any treatment-related liver function test abnormality that meets the following criteria require discontinuation:
 - AST or ALT $> 5 \times$ ULN to $8 \times$ ULN for > 2 weeks
 - AST or ALT $> 8 \times$ ULN
 - Total bilirubin $> 5 \times$ ULN
 - Concurrent AST or ALT $> 3 \times$ ULN and total bilirubin $> 2 \times$ ULN
- Grade 3 or 4 infusion reaction of any duration
- Any Grade 4 treatment -related AE or laboratory abnormality, except for the following events, which do not require discontinuation:
 - Grade 4 neutropenia ≤ 7 days.

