6.3.2 Hepatobiliary Disorders or Events

Eligible patients must have adequate liver function, as manifested by measurements of total bilirubin and hepatic transaminases, and liver function will be monitored throughout study treatment. Management guidelines for hepatic events are provided in the table below.

Patients with right upper-quadrant abdominal pain and/or unexplained nausea or vomiting should have liver function tests (LFTs) performed immediately and reviewed before administration of the next dose of study drug(s).

For patients with elevated LFTs, concurrent medication, viral hepatitis, and toxic or neoplastic etiologies should be considered and addressed, as appropriate.

Management Guidelines for Hepatobiliary Disorders or Events

| Event | Management |
|---|--|
| Hepatobiliary disorder or event, Grade 1 | 
 ● Continue atezolizumab and tiragolumab. ● Monitor LFTs until values resolve to within normal limits or to baseline values. |
| Hepatobiliary disorder or event, Grade 2 | 
All events:
 
 ● Monitor LFTs more frequently until return to baseline values. 
Events of > 5 days' duration:
 
 ● Withhold atezolizumab and tiragolumab for up to 12 weeks after event onset.^a ● Initiate treatment with corticosteroids equivalent to 1–2 mg/kg/day oral prednisone. ● If event resolves to Grade 1 or better, resume atezolizumab and tiragolumab.^b ● If event does not resolve to Grade 1 or better while withholding atezolizumab and tiragolumab, permanently discontinue atezolizumab and tiragolumab.^c |
| Hepatobiliary disorder or event, Grade 3 or 4 | 
 ● Permanently discontinue atezolizumab and tiragolumab.^c ● Consider patient referral to gastrointestinal specialist for evaluation and liver biopsy to establish etiology of hepatic injury. ● Initiate treatment with corticosteroids equivalent to 1–2 mg/kg/day oral prednisone. ● If event does not improve within 48 hours after initiating corticosteroids, consider adding an immunosuppressive agent. 
If event resolves to Grade 1 or better, taper corticosteroids over ≥ 1 month.
 |

LFT = liver function test.

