- ^a Atezolizumab and tiragolumab may be withheld for a longer period of time (i.e., > 12 weeks after event onset) to allow for corticosteroids (if initiated) to be reduced to the equivalent of ≤ 10 mg/day oral prednisone. The acceptable length of the extended period of time must be based on the investigator's benefit-risk assessment and in alignment with the protocol requirements for the duration of treatment and documented by the investigator.
- ^b If corticosteroids have been initiated, they must be tapered over ≥ 1 month to the equivalent of ≤ 10 mg/day oral prednisone before atezolizumab and tiragolumab can be resumed.
- ^c Resumption of atezolizumab and tiragolumab may be considered in patients who are deriving benefit and have fully recovered from the immune-mediated event. The decision to re-challenge patients with atezolizumab should be based on the investigator's benefit-risk assessment and documented by the investigator.

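### Sections 6.2.1 and 6.3.2 give different instructions for raised liver tests and different routes back to treatment, and neither is said to prevail

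*Combined protocol and SAP*

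**What the plan says.** Section 6.2.1 contains three statements that bear on liver tests.

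- **Laboratory exception.** One bullet stops treatment for Grade 3 or higher non-skin related events that last more than 7 days or recur, and then lists exceptions. One exception reads "Grade 3 treatment-related laboratory abnormalities do not require treatment discontinuation except", followed by "Grade 3 treatment-related thrombocytopenia > 7 days or associated with clinically significant bleeding requires discontinuation". AST and ALT are not mentioned there.
- **Grade 3 AST/ALT.** A later bullet says "In most cases of Grade 3 AST or ALT elevation, study treatment will be permanently discontinued". If the investigator sees a favorable benefit/risk for continuing, "a discussion between the Investigator and the Medical Monitor/designee must occur".
- **Liver-test list.** "Any treatment-related liver function test abnormality that meets the following criteria require discontinuation". The list has four entries: AST or ALT above 5 and up to 8 × ULN for more than 2 weeks; AST or ALT above 8 × ULN; total bilirubin above 5 × ULN; and AST or ALT above 3 × ULN concurrent with total bilirubin above 2 × ULN. No exception or resumption route is attached.

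Section 6.3.2 is a table by grade. At Grade 2, liver tests are monitored more often. If the event lasts more than 5 days, both drugs are withheld for up to 12 weeks and resumed once it is back to Grade 1 or better. In the row "Hepatobiliary disorder or event, Grade 3 or 4" both drugs are permanently discontinued, with a pointer to footnote c. That footnote says "Resumption of atezolizumab and tiragolumab may be considered in patients who are deriving benefit and have fully recovered from the immune-mediated event", and rests the re-challenge decision on the investigator's documented benefit-risk assessment.

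**The concern.** Both sections are written as instructions, and a site may open either one when a liver result comes back. If they lead to different actions, management depends on which page was read.

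The result that matters most is a transaminase rise with a bilirubin rise. Section 7.1.3.1 lists raised ALT or AST with raised bilirubin or jaundice (Hy's Law) as an adverse event of special interest, reportable within 24 hours. Section 6.2.1 makes its version of that pattern a mandatory stop, yet the hepatic table in Section 6.3.2 does not mention it.

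There is also a data consequence. Section 2 includes discontinuations due to treatment-related adverse events in the safety endpoint. Under Section 5.3, a patient who stops before C3D1 is replaced in Stage 1 but not in Stage 2. Both depend on a stopping decision that the protocol does not define consistently.

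**Working it through.** No sample size, error rate or event count is involved, so there is no figure to reproduce. The check applies each section to the same liver result and compares the action and the route back.

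| Treatment-related liver result | Section 6.2.1 | Section 6.3.2 | Agreement |
|---|---|---|---|
| AST/ALT > 3 × ULN with bilirubin > 2 × ULN | Discontinue; no duration, grade or route back stated | No entry. If each value is Grade 2: monitor, hold once past 5 days, resume at Grade 1 or better. If either is Grade 3: permanently discontinue, with footnote c | Conflict if both are Grade 2; otherwise same action, different route back |
| Grade 3 AST/ALT | Discontinue in most cases; continuing needs a Medical Monitor discussion | Permanently discontinue in all cases; investigator may re-challenge after full recovery | Both lean to stopping; scope and approver differ |
| AST/ALT > 5 to 8 × ULN for 2 weeks or less | This list entry is not yet met | If Grade 3: permanently discontinue at once. If Grade 2: the Grade 2 row | Awkward, by implication only |
| Any other pattern on the 6.2.1 list | Discontinue; no route back stated | Footnote c allows resumption even after permanent discontinuation | Route back differs |

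**Step 1: combined pattern.** Take ALT 4 × ULN and bilirubin 2.5 × ULN. Since 4 > 3 and 2.5 > 2, Section 6.2.1 requires a stop. Section 6.3.2 has to be read by grade. The protocol names CTCAE v5.0 but does not print its cut-offs, so I assume that each value is Grade 2 with normal baselines. On that assumption the table gives closer monitoring for 5 days, then a hold, then an instruction to resume on recovery. That is the opposite of the stop in Section 6.2.1.

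**Step 2: Grade 3 AST/ALT.** This comparison needs no outside cut-off. Section 6.2.1 allows some patients to continue without stopping, after a Medical Monitor discussion. Section 6.3.2 allows none to continue, but lets the investigator restart treatment later. Its hepatic rows do not mention the Medical Monitor, although the Grade 3 or 4 pulmonary row (Section 6.3.1) and the diarrhea/colitis rows for Grades 2 to 4 (Section 6.3.3) do.

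**Step 3: duration criterion.** Take ALT 6 × ULN for 10 days. It lies in the 5 to 8 range, but 10 days is less than 14, so that entry of the list is not met. If 6 × ULN is Grade 3 (same assumption), Section 6.3.2 stops at once. The list states what is sufficient for stopping, not what is necessary, so this is not a direct contradiction. A 2-week allowance simply has little purpose beside an immediate Grade 3 stop.

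**Step 4: precedence.** None of the liver text in Sections 6.2, 6.2.1 or 6.3.2 says which section governs. Section 6.0 gives the PI discretion over holds and modifications beyond those described, which does not rank the ones that are described.

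**The case against.** The best defence is that Section 6.2.1 lists independent stop criteria, any one of which is enough. On that reading the Grade 3 laboratory exception only relaxes the general 7-day bullet it belongs to. The AST/ALT bullet and the liver-test list then stand on their own as more specific rules, and silence in Section 6.3.2 does not cancel an explicit stop elsewhere. Section 6.2.1 also stops treatment for any laboratory abnormality that the investigator judges a substantial clinical risk.

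Much of this stands. A reader might infer that one Grade 3 AST/ALT result can mean continue, hold and resume, or stop permanently. The documents do not support that:

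- Saying that discontinuation is not required is not an instruction to continue, and the laboratory line sits under the 7-day bullet.
- The liver-test list never says that its conditions are the only ones.
- Hold-and-resume is the Grade 2 row of Section 6.3.2.
- The AST/ALT bullet and the Grade 3 or 4 row both point to stopping.

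It would also be too strong to call the laboratory exception a flat contradiction of the AST/ALT bullet. The text does not say whether AST/ALT falls inside the exception, and the bullet indentation in the text I had is not reliable enough to settle it.

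The defence does not remove the rest. Section 6.3.2 says resume, or permits re-challenge, where Section 6.2.1 requires a stop with no route back. The approval routes differ, and a site would have to supply the precedence rule itself.

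On the data side, Section 14.3 and the Protocol Summary define safety by treatment-related Grade 3 or higher events without discontinuations, and the stopping rule in Section 14.7.1 also counts events. The effect on results is therefore limited to the discontinuation count in Section 2 and replacement before C3D1.

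**Conclusion.** The concern holds as a failure of two sections to agree:

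1. For the patterns on the Section 6.2.1 list, including the combined AST/ALT and bilirubin pattern, one section requires a stop with no route back. The other has no entry for the combination and allows resumption even after permanent discontinuation.
2. For Grade 3 AST/ALT, the sections differ on whether every case stops and on who decides about continuing or restarting. Whether AST/ALT belongs to the laboratory exception is left open.

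The second item and the footnote c difference rest on the protocol's wording alone. The direct stop-versus-resume conflict for the combined pattern rests on the assumption that both values are Grade 2. The duration point is by implication only.

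The main consequence is patient safety: a site following Section 6.3.2 alone could re-dose a patient whom Section 6.2.1 requires to stop. The discontinuation count could differ between sites, by an amount that cannot be estimated from the documents.

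**What to change.** The sponsor should reconcile Section 6.2.1 with Section 6.3.2 and its footnote c, so that the same liver result leads to the same action and the same approval route in both. The reconciled text should cover the combined AST/ALT-plus-bilirubin case and say whether AST/ALT is inside or outside the Grade 3 laboratory exception. Alternatively, the protocol can state which section prevails. The rule and its thresholds are for the sponsor to decide; no view is taken here on which is right.

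The cost is amendment wording in two sections. The schedule of activities already has a CMP on Day 1 of every cycle, so reconciling the wording does not in itself add a scheduled test.

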6.3 Management Guidelines for Atezolizumab- and Tiragolumab-Specific Adverse Events

6.3.1 Respiratory Disorders and Pulmonary Events

Immune-mediated pulmonary events are a potential risk with tiragolumab.

Pulmonary events may present as new or worsening cough, chest pain, fever, dyspnea, fatigue, hypoxia, pneumonitis, and pulmonary infiltrates. Patients will be assessed for pulmonary signs and symptoms throughout the study.

All pulmonary events should be thoroughly evaluated for other commonly reported etiologies such as pneumonia or other infection, lymphangitic carcinomatosis, pulmonary embolism, heart failure, chronic obstructive pulmonary disease, or pulmonary hypertension. COVID-19 evaluation should be performed per institutional guidelines where relevant. Management guidelines for pulmonary events are provided in the table below.

Management Guidelines for Respiratory Disorders and Pulmonary Events, Including Pneumonitis

| Event | Management |
|--|--|
| Respiratory disorder or other pulmonary event, Grade 1 | 
 • Continue atezolizumab and tiragolumab and monitor closely. • Re-evaluate on serial imaging. • Consider patient referral to pulmonary specialist. |
| Respiratory disorder or other pulmonary event, Grade 2 | 
 • Withhold atezolizumab and tiragolumab for up to 12 weeks after event onset.^a • Refer patient to pulmonary and infectious disease specialists and consider bronchoscopy or BAL with or without transbronchial biopsy. • Initiate treatment with corticosteroids equivalent to 1–2 mg/kg/day oral prednisone. • If event resolves to Grade 1 or better, resume atezolizumab and tiragolumab.^b |

| Event | Management |
|---|---|
| | 
 ● If event does not resolve to Grade 1 or better while withholding atezolizumab and tiragolumab, permanently discontinue atezolizumab and tiragolumab and contact Medical Monitor. ^c ● For recurrent events, treat as a Grade 3 or 4 event. |
| Respiratory disorder or other pulmonary event, Grade 3 or 4 | 
 ● Permanently discontinue atezolizumab and tiragolumab and contact Medical Monitor. ^c 
 ● Oral or IV broad-spectrum antibiotics should be administered in parallel to the immunosuppressive treatment. ● Bronchoscopy or BAL with or without transbronchial biopsy is recommended. ● Initiate treatment with corticosteroids equivalent to 1–2 mg/kg/day oral prednisone. ● If event does not improve within 48 hours after initiating corticosteroids, consider adding an immunosuppressive agent. ● If event resolves to Grade 1 or better, taper corticosteroids over ≥ 1 month. |

BAL = bronchoscopic alveolar lavage.

^a Atezolizumab and tiragolumab may be withheld for a longer period of time (i.e., > 12 weeks after event onset) to allow for corticosteroids (if initiated) to be reduced to the equivalent of ≤ 10 mg/day oral prednisone. The acceptable length of the extended period of time must be based on the investigator's benefit risk assessment and in alignment with the protocol requirements for the duration of treatment and document by the investigator.

^b If corticosteroids have been initiated, they must be tapered over ≥ 1 month to the equivalent of ≤ 10 mg/day oral prednisone before atezolizumab and tiragolumab can be resumed.

^c Resumption of atezolizumab may be considered in patients who are deriving benefit and have fully recovered from the immune-mediated event. The decision to re challenge patients with atezolizumab should be based on the investigator's assessment of benefit risk assessment and documented by the investigator (or appropriate delegate).

^d In case of pneumonitis, atezolizumab should not be resumed after permanent discontinuation.

6.3.2 Hepatobiliary Disorders or Events

Eligible patients must have adequate liver function, as manifested by measurements of total bilirubin and hepatic transaminases, and liver function will be monitored throughout study treatment. Management guidelines for hepatic events are provided in the table below.

Patients with right upper-quadrant abdominal pain and/or unexplained nausea or vomiting should have liver function tests (LFTs) performed immediately and reviewed before administration of the next dose of study drug(s).

For patients with elevated LFTs, concurrent medication, viral hepatitis, and toxic or neoplastic etiologies should be considered and addressed, as appropriate.

Management Guidelines for Hepatobiliary Disorders or Events

| Event | Management |
|---|--|
| Hepatobiliary disorder or event, Grade 1 | 
 ● Continue atezolizumab and tiragolumab. ● Monitor LFTs until values resolve to within normal limits or to baseline values. |
| Hepatobiliary disorder or event, Grade 2 | 
All events:
 
 ● Monitor LFTs more frequently until return to baseline values. 
Events of > 5 days' duration:
 
 ● Withhold atezolizumab and tiragolumab for up to 12 weeks after event onset.^a ● Initiate treatment with corticosteroids equivalent to 1–2 mg/kg/day oral prednisone. ● If event resolves to Grade 1 or better, resume atezolizumab and tiragolumab.^b ● If event does not resolve to Grade 1 or better while withholding atezolizumab and tiragolumab, permanently discontinue atezolizumab and tiragolumab.^c |
| Hepatobiliary disorder or event, Grade 3 or 4 | 
 ● Permanently discontinue atezolizumab and tiragolumab.^c ● Consider patient referral to gastrointestinal specialist for evaluation and liver biopsy to establish etiology of hepatic injury. ● Initiate treatment with corticosteroids equivalent to 1–2 mg/kg/day oral prednisone. ● If event does not improve within 48 hours after initiating corticosteroids, consider adding an immunosuppressive agent. 
If event resolves to Grade 1 or better, taper corticosteroids over ≥ 1 month.
 |

LFT = liver function test.

- ^a Atezolizumab and tiragolumab may be withheld for a longer period of time (i.e., > 12 weeks after event onset) to allow for corticosteroids (if initiated) to be reduced to the equivalent of ≤ 10 mg/day oral prednisone. The acceptable length of the extended period of time must be based on the investigator's benefit-risk assessment and in alignment with the protocol requirements for the duration of treatment and documented by the investigator.
- ^b If corticosteroids have been initiated, they must be tapered over ≥ 1 month to the equivalent of ≤ 10 mg/day oral prednisone before atezolizumab and tiragolumab can be resumed.
- ^c Resumption of atezolizumab and tiragolumab may be considered in patients who are deriving benefit and have fully recovered from the immune-mediated event. The decision to re-challenge patients with atezolizumab should be based on the investigator's benefit-risk assessment and documented by the investigator.

6.3.3 Gastrointestinal Disorders or Events

Immune-mediated gastrointestinal events are a potential risk with tiragolumab.

Management guidelines for diarrhea or colitis are provided in the table below.

All events of diarrhea or colitis should be thoroughly evaluated for other more common etiologies. For events of significant duration or magnitude or associated with signs of systemic inflammation or acute-phase reactants (e.g., increased C-reactive protein, platelet count, or bandemia): Perform sigmoidoscopy (or colonoscopy, if appropriate) with colonic biopsy, with three to five specimens for

standard paraffin block to check for inflammation and lymphocytic infiltrates to confirm colitis diagnosis.

Management Guidelines for Gastrointestinal Disorders or Events (Diarrhea or Colitis)

| Event | Management |
|------------------------------|---|
| Diarrhea or colitis, Grade 1 | 
 ● Continue atezolizumab and tiragolumab. ● Initiate symptomatic treatment. ● Endoscopy is recommended if symptoms persist for > 7 days. ● Monitor closely. |
| Diarrhea or colitis, Grade 2 | 
 ● Withhold atezolizumab and tiragolumab for up to 12 weeks after event onset.^a ● Initiate symptomatic treatment. ● If strong clinical suspicion for immune-mediated colitis, start empiric IV steroids while waiting for definitive diagnosis. ● Patient referral to GI specialist is recommended. ● For recurrent events or events that persist > 5 days, initiate treatment with corticosteroids equivalent to 1–2 mg/kg/day oral prednisone. If the event does not improve within 48 hours after initiating corticosteroids, consider adding an immunosuppressive agent. ● If event resolves to Grade 1 or better, resume atezolizumab and tiragolumab.^b ● If event does not resolve to Grade 1 or better while withholding atezolizumab and tiragolumab, permanently discontinue atezolizumab and tiragolumab and contact Medical Monitor.^c |
| Diarrhea or colitis, Grade 3 | 
 ● Withhold atezolizumab and tiragolumab for up to 12 weeks after event onset.^a ● Refer patient to GI specialist for evaluation and confirmatory biopsy. ● Initiate treatment with corticosteroids equivalent to 1–2 mg/kg/day IV methylprednisolone and convert to 1–2 mg/kg/day oral prednisone or equivalent upon improvement. If event does not improve within 48 hours after initiating corticosteroids, consider adding an immunosuppressive agent. ● If event resolves to Grade 1 or better, resume atezolizumab and tiragolumab.^b ● If event does not resolve to Grade 1 or better while withholding atezolizumab and tiragolumab, permanently discontinue atezolizumab and tiragolumab and contact Medical Monitor.^c |
| Diarrhea or colitis, Grade 4 | 
 ● Permanently discontinue atezolizumab and tiragolumab and contact Medical Monitor.^c ● Refer patient to GI specialist for evaluation and confirmatory biopsy. ● Initiate treatment with corticosteroids equivalent to 1–2 mg/kg/day IV methylprednisolone and convert to 1–2 mg/kg/day oral prednisone or equivalent upon improvement. ● If event does not improve within 48 hours after initiating corticosteroids, consider adding an immunosuppressive agent. ● If event resolves to Grade 1 or better, taper corticosteroids over \geq 1 month. |

| Event | Management |
|-------|------------|
|-------|------------|

GI = gastrointestinal.

- ^a Atezolizumab and tiragolumab may be withheld for a longer period of time (i.e., > 12 weeks after event onset) to allow for corticosteroids (if initiated) to be reduced to the equivalent of ≤ 10 mg/day oral prednisone. The acceptable length of the extended period of time must be based on the investigator's benefit-risk assessment and in alignment with the protocol requirements for the duration of treatment and documented by the investigator.
- ^b If corticosteroids have been initiated, they must be tapered over ≥ 1 month to the equivalent of ≤ 10 mg/day oral prednisone before atezolizumab and tiragolumab can be resumed.
- ^c Resumption of atezolizumab and tiragolumab may be considered in patients who are deriving benefit and have fully recovered from the immune-mediated event. Patients can be re-challenged with atezolizumab and tiragolumab only after approval has been documented by the investigator.

